6.4 Analysis Population Set Determination Details

(1) No Enlite Sensor inserted: Subjects obtain randomization number, but have no Enlite Sensor inserted.

(2) No paired Enlite Sensor and YSI measurement: Subjects obtain randomization number and have a Enlite Sensor inserted, but have no paired Enlite Sensor and YSI measurement.

(3) Violation of Inclusion/Exclusion criteria: Subjects do not meet the inclusion criteria or meet the exclusion criteria pre-specified in the protocol, and this protocol deviation may severely affect the results of primary effective endpoint. Whether protocol deviation severely affect the results of primary effective endpoints will be judged together by sponsor, investigators and statistician through discussion;

(4) $FAS^{#1}$ = Number of the randomized subjects – Number of subjects who have no Enlite Sensor inserted;

$FAS^{#2}$ = Number of $FAS^{#1}$ – Number of subjects who have no paired Enlite Sensor and YSI measurement;

PPS = Number of $FAS^{#2}$ - Number of subjects who severely violate study protocol (i.e. violate inclusion and exclusion criteria, etc.).

The listing of subjects who have no Enlite Sensor inserted or severely violate study protocol will be listed, including the center number, registration number, gender, age, type, details, $FAS^{#1}$, $FAS^{#2}$ and PPS.

6.5 Missing Values, Abnormal Value and Outliers

Data entry error or non-reasonable values will be cleaned before data analysis. No imputations will be done for missing data.

All withdrawals subjects will be included in the final statistical analysis. For the missing primary endpoint data due to early withdrawal, no imputations will be done for missing data.

For the dates collected during the trail, if the day or month or year is filled with "UK" or "NA" , they will not be processed.

6.6 General Considerations for Data Analysis

6.6.1 Data Collection

(1) Primary endpoint, secondary endpoints, and other descriptive endpoints will be based on retrospective data collected from primary sensor.

(2) Precision analysis will be based on data collected from both sensors.

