9.2.6. Visit 5: End of Study

- Subjects will return to the clinic to remove their study devices
- Investigational Center staff will review documentation of time they calculated for T=145 hours where the sensor may be removed at that time or after that time to ensure that the devices are not removed pre-maturely
- Investigational center staff will address questions or concerns from subjects
- Investigational center staff will ask subjects about the occurrence of any AEs or device deficiencies.
- Investigational center staff will:

- Download the iPro2 data from CareLink iPro following completion of the study devices wear
- Obtain subject's Study Meter BG values and enter into CareLink iPro
- Collect subject's Patient Log Sheet
- Provide iPro2 data to sponsor
- Investigational center staff will perform a Skin assessment on the area of each of the Enlite Sensor insertion sites and document in subject source and complete the Skin Assessment eCRFs
- Investigational center staff will collect returned devices (See Table 1 in Device Accountability section) and unused supplies from subjects
- Subjects will complete a questionnaire about their Enlite Sensor experience.
- Primary sensor and secondary sensor will be randomly assigned via RDC.
- An Exit eCRF will be completed at this visit.

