9.4. Randomization and Treatment Assignment

Investigational Centers will receive this randomization assignment generated electronically in the study database from Medtronic. The first randomization scheme assigns the subjects to one of the following sensor wear days (Day 1, 3-4, or 6) which determines when they will be participating in the in-clinic YSI FST.

Once subject is assigned to the study group, subjects will stay in that randomization group during the study.

In addition, at the end of the study (Visit 5), another randomization scheme will be done to assign the primary and secondary sensor for each subject.

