5.1 Study Design

This study is a multi-center, randomized, prospective single-sample correlational design without controls. Up to 72 subjects will be enrolled in order to have approximately 60 subjects complete the study. Three investigational centers in China will be used during this study.

Each subject will wear the following devices:

- Two Enlite Sensors each connected to an iPro2 for approximately 6 days

Sensor Location:

- The 2 Enlite Sensors will be worn in the abdomen area. Investigational center staff will insert sensors and connect to the iPro2s.

During the study, each subject will be randomized and undergo one Yellow Springs Instrument (YSI™) frequent sample testing (FST) (Day 1, 3-4, or 6).

On the evening prior to FST, subjects will be asked to fast for approximately 12 hours and adjust their insulin and medications according to routine care (for example as they would do for fasting lipid panel). Subjects may fast for shorter period of time **based on investigator discretion**.

The subject should be in fasting status upon arrival hospital to start FST process. **The feeding protocol may be modified based on investigator discretion**. The duration of FST will be approximately 7 hours.

During the study, subjects will continue with their current diabetes regimen independent of the study devices. Subjects will be instructed by the investigational center that they are not to use the study devices (except for the study meter) for the management of their diabetes. The Study Meter may be used for treatment decisions and calibration of Enlite Sensor.

Fingerstick Testing: A minimum of 4 fingerstick glucose readings per day will be requested for subjects. Subjects should test prior to meals and at bedtime.

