6.2 Sample Size Determination

The sample size selected is based on the primary effectiveness endpoint (i.e., accuracy), agreement in comparative readings of paired sensor and YSI glucose readings.

Based on pervious study, using one sample T test (formula provided below) with α level of 0.975 (one sided), β of 0.8, μ_0 is 0.6, μ_α is 0.72 and σ is 0.32:

$$n = \sigma^2 \frac{(t_\alpha + t_\beta)^2}{(\mu_0 - \mu_\alpha)^2}$$

it is indicated that a sample size of 58 will have power greater than or equal to 80% to demonstrate that the overall agreement rate is greater than 0.6. Considering 20% drop out, we need to enroll 72 subjects.

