6.6.2 Pairing Scheme

(1) All YSI and fingerstick values collected will be presented. Most of descriptive analyses will include all YSI values, such as those less than ($<$) 40 mg/dL, or greater than ($>$) 400 mg/dL as long as Enlite Sensor values are greater than or equal to (\geq) 40 mg/dL or less than or equal to (\leq) 400 mg/dL (displayed to users as Low or High without numerical numbers).

Reference glucose values (YSI values or fingerstick values) will be paired with the closest Enlite Sensor value between [0, 5) minutes.

(2) The primary Enlite Sensor will be used as a reference for precision analysis. Reference glucose values (primary Enlite Sensor) will be paired with the closest Enlite Sensor value between [0, 5) minutes

(3) Clarke EGA will be restricted to YSI values of 40-400 mg/dL. The same pairing scheme will be utilized.

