7.6 Primary Endpoint

For the primary endpoint 20/20% consistency rate analysis, both the analyses based on measurement level and subject level will be provided. One sample T test will be used for the analysis of the primary endpoint based on subject level. Both the approximate normal distribution method and Clopper-Pearson method will be used to estimate primary endpoint based on measurement level. The 95% confidence limit of mean agreement rate will be calculated and tested against corresponding threshold pre-specified in protocol.

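### Optional improvement: the primary t-test uses one randomly drawn sensor per subject; averaging the two sensors' agreement rates would add power from data already collected

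*SAP*

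**What the plan says.** SAP 5.1 has each subject wear "Two Enlite Sensors each connected to an iPro2 for approximately 6 days", both in the abdomen. After wear is complete, Protocol 9.4 states that "another randomization scheme will be done to assign the primary and secondary sensor for each subject", and Protocol 9.2.6 places this at the last visit: "Primary sensor and secondary sensor will be randomly assigned via RDC". The draw ratio is not stated.

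SAP 6.6.1 then limits the endpoints: "Primary endpoint, secondary endpoints, and other descriptive endpoints will be based on retrospective data collected from primary sensor". Protocol 14.8.1 says the same, and the endpoint definitions in Protocol 5.2.1 and SAP 5.2 also name the primary sensor.

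For the test, SAP 7.6 says "One sample T test will be used for the analysis of the primary endpoint based on subject level". It adds estimates that pool all readings: "Both the approximate normal distribution method and Clopper-Pearson method will be used to estimate primary endpoint based on measurement level". Under Protocol 14.9 the study succeeds if the 97.5% lower confidence limit exceeds 60%.

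The second sensor's stated use is the precision analysis, where "The primary Enlite Sensor will be used as a reference for precision analysis" (SAP 6.6.2). The exception is an unspecific mention of all devices in the descriptive YSI subgroup analyses (Protocol 5.2.3, SAP 7.9). No section explains why the second sensor is left out of the primary test.

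**The concern.** The second sensor is already worn, downloaded and set against the same YSI samples. Leaving it out means the pass/fail limit carries avoidable variance from the choice of sensor. The sample size leaves little reserve: SAP 6.2 says "it is indicated that a sample size of 58 will have power greater than or equal to 80" percent, and 58 is the smallest number for which that is true. What is at stake is some extra power in the deciding test, at no cost in subjects, visits or blood samples.

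**Working it through.** **Inputs.** From SAP 6.2 and Protocol 14.5: null rate 0.60, alternative 0.72, SD 0.32, n = 58. From SAP 6.9: one-sided 0.025. The SD is read as the between-subject SD of a single sensor's agreement rate.

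**Reproducing the plan's figure.** For a one-sample t-test, power comes from the noncentral t distribution with n−1 degrees of freedom and noncentrality (0.72 − 0.60)/0.32 × √n. At n = 57 power is 79.5%; at n = 58 it is 80.2%. The stated 58 is confirmed.

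**Effect of averaging.** Let A and B be a subject's two agreement rates. Assume a 1:1 draw, equal variances σ² and correlation r.

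- Expectation: the drawn rate has mean (E[A] + E[B])/2, which is also the mean of (A + B)/2. The hypothesis and the 60% threshold are unchanged.
- Variance: Var[(A + B)/2] = (σ² + σ² + 2rσ²)/4 = σ²(1 + r)/2.

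This holds for averaging the two rates. Averaging the two glucose readings before scoring would define a different quantity.

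**Power if every subject has YSI pairs from both sensors.** SD of the average = 0.32 × √((1 + r)/2).

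| r | SD | n=58, rate 0.72 | n=60, rate 0.72 | n=58, rate 0.75 |
|---|---|---|---|---|
| one sensor (or r=1) | 0.320 | 80.2% | 81.5% | 93.9% |
| 0.9 | 0.312 | 82.1% | 83.4% | 95.0% |
| 0.8 | 0.304 | 84.1% | 85.4% | 95.9% |
| 0.7 | 0.295 | 86.1% | 87.3% | 96.8% |
| 0.5 | 0.277 | 90.0% | 91.0% | 98.2% |

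The distance from the mean to the 97.5% lower limit at n = 58 is 8.4 percentage points with one sensor, against 8.2, 8.0, 7.8 and 7.3 points at r = 0.9, 0.8, 0.7 and 0.5.

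**Bounded data.** Agreement rates lie between 0 and 1, so the comparison was repeated with beta-distributed rates (SD 0.32, n = 58, 40,000 trials). At a true rate of 0.72, power was about 78% with one sensor. Averaged, it was 87.9%, 83.7%, 81.4% and 79.7% at observed correlations of 0.49, 0.69, 0.80 and 0.91. At a true rate of 0.60 the type I error was 2.9% to 3.1% with one sensor and 2.9% averaged, so averaging does not inflate it.

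**Subjects with only one paired sensor.** Let f be their share and m their mean rate, with 0.72 in everyone else. Two rules are possible.

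- Drawn-sensor rule (the subject counts only if the working sensor is drawn): target = [(1−f)0.72 + (f/2)m]/(1−f/2).
- Available-sensor rule (the working sensor is always used): target = (1−f)0.72 + f·m.

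With f = 0.10 and m = 0.60 (both assumed), the targets are 0.678/0.95 = 0.714 and 0.648 + 0.060 = 0.708. With m = 0.50 they are 0.673/0.95 = 0.708 and 0.648 + 0.050 = 0.698. The available-sensor rule therefore moves the target.

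Simulated power (normal model, 58 subjects with any pair):

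- f = 0.10, m = 0.60: the drawn sensor gives 73%. Averaging with the available-sensor rule gives 81%, 77%, 75% and 73% at r = 0.5, 0.7, 0.8 and 0.9.
- f = 0.10, m = 0.50, r = 0.9: the drawn sensor gives 68%. Averaging with the available-sensor rule gives 63%. Averaging only where both sensors are paired, with the drawn-sensor rule otherwise, gives about 70%.

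**The case against.** **Nothing is broken.** The draw is prespecified, the test is valid and the stated power is met. A reader might infer that the primary analysis is biased or underpowered; the documents support neither. Protocol 16.7 also expects a rate significantly above 60%, and the gain shrinks as the true rate moves above 72%. This stands, and it makes the point optional.

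**The Visit 5 draw as a lottery.** A reader might infer that drawing the sensor after the data exist is a harm of its own, because another draw could change the verdict. It is not. The trial makes one planned draw and the t-test already carries its variance, so this only restates the variance difference above.

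**The gain is unknown.** The same subject, body region, YSI session and meter calibration suggest that r may be high, and at r = 0.9 the gain is about 2 points. This stands.

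**Averaging could lose power.** It can if the working sensor is always used when the other has no pairs, as shown above. That argues against the available-sensor rule as primary, not against averaging where both sensors are paired. Protocol 9.6 has both sensors re-inserted once if either dislodges before the YSI session or within its first 5 hours, which should limit such cases. How they are handled now is itself an inference: Protocol 14.6 and SAP 6.3 ask for one sensor-YSI pair without saying that it must come from the primary sensor.

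**Cost and coherence.** The change redefines the primary variable in a registration study and would put the subject-level and measurement-level results of SAP 7.6 on different sensor sets. SAP 7.7 and 7.13 refer to a regulatory guideline that cannot be consulted here, so whether it expects one designated sensor is unknown. These are real costs for the sponsor to weigh.

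**Conclusion.** Optional improvement, not an error. Averaging the two agreement rates where both sensors have YSI pairs keeps the target and the 60% threshold and reduces the variance by the factor (1 + r)/2. At the planned effect and n = 58, the gain over 80.2% is 9.8, 5.9, 3.9 or 1.9 percentage points at r = 0.5, 0.7, 0.8 or 0.9, and nil at r = 1.

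These figures assume that 0.32 is the single-sensor SD, that the two sensors have equal variance, that the draw is 1:1 and that both sensors are paired in every subject. None of these is stated in the documents, and r is not given. The direction is secure under the 1:1 draw; the size is not.

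**What to change.** Before database lock, and before anyone sees sensor-YSI agreement:

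1. Define the subject-level primary value as the mean of the two sensors' agreement rates when both sensors have YSI pairs. Average rates, not glucose readings.
2. When only one sensor has pairs, apply the drawn-sensor rule explicitly: the subject contributes only if the drawn sensor has pairs. Report how many such subjects there are.
3. Keep the one-sample t-test, the 97.5% lower limit and the 60% threshold.
4. As sensitivity analyses, run the drawn-sensor t-test in all subjects and, separately, the available-sensor rule.
5. State that the measurement-level estimates, the secondary endpoints and the precision reference stay on the drawn sensor.

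Make the edit everywhere the primary endpoint names the primary sensor or sets out its test: the Protocol synopsis, 5.2.1, 14.8.1 and 14.9; SAP 5.2, 6.6.1 and 7.6. Changing only the analysis sections would leave them in conflict with the endpoint definition.

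**Cost.** No new data, visits or subjects. Protocol 16.10 requires a justified amendment with ethics committee approval, and regulator approval if applicable, before it is implemented. The report must explain that the subject-level and measurement-level results use different sensor sets. If r is near 1, little is gained for this effort.

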6.6.2 Pairing Scheme

(1) All YSI and fingerstick values collected will be presented. Most of descriptive analyses will include all YSI values, such as those less than ($<$) 40 mg/dL, or greater than ($>$) 400 mg/dL as long as Enlite Sensor values are greater than or equal to (\geq) 40 mg/dL or less than or equal to (\leq) 400 mg/dL (displayed to users as Low or High without numerical numbers).

Reference glucose values (YSI values or fingerstick values) will be paired with the closest Enlite Sensor value between [0, 5) minutes.

(2) The primary Enlite Sensor will be used as a reference for precision analysis. Reference glucose values (primary Enlite Sensor) will be paired with the closest Enlite Sensor value between [0, 5) minutes

(3) Clarke EGA will be restricted to YSI values of 40-400 mg/dL. The same pairing scheme will be utilized.

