7.2.4. CareLink™ iPro Therapy Management Software for Diabetes (MMT-7340) - Desktop Software

CareLink iPro Therapy Management Software for Diabetes(MMT-7340), referred to as CareLink iPro in the CIP, is a PC-based software desktop application. Refer to 10572826DOC for the software version. It will manage the data flow to and from the iPro2; merge sensor and BG meter data to produce glucose sensor values; produce user-friendly graphics and text displaying the data downloaded from the iPro2; store the data on computer and allow for data retrieval in both graphical and textual format.

This software receives the uploaded data via the hardware physical port (USB) of the recorder dock processes and analyzes the uploaded data, and finally generates reports.

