14.9. Statistical Model and Analyses of Primary Endpoint

Sensor values from primary sensor will be compared to YSI plasma glucose values during YSI FSTs. A within 20% mean agreement rate (± 20 mg/dL (1.1 mmol/L) when Reference BG less than or equal to (\leq) 80 mg/dL (4.4 mmol/L) between Enlite Sensor values and YSI plasma glucose values during YSI FST days defined as μ will be evaluated against the null Hypothesis:

$$H_0: \mu \leq 60\%$$

$$H_1: \mu > 60\%$$

- Statistical testing

One sample T test will be used for the analysis of the primary endpoint. The 97.5% lower confidence limit of the mean agreement rate will be tested against corresponding threshold.

- Missing data
No imputation for missing data will be performed.
- Pass/Fail Criteria
The study pass/fail criteria is based on statistical hypothesis of the primary endpoint. If the 97.5% lower confidence limit is greater than 60%, the study will be considered as success.
- Justification for Exclusion of Particular Information from the testing of the Hypothesis
Not Applicable

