5.2 Primary Endpoint

The primary endpoint is 20/20% consistency evaluation with the reference value which is expressed by the agreement rate.

Sensor values from primary sensor will be compared to YSI plasma glucose values during YSI FSTs to analyze the agreement rate. Consistency rate = A + B:

A = (the number of pairs of the deviation of sensor value from primary sensor minus YSI value is within $\pm 20\%$ /total number of pairs) * 100% (when the blood glucose concentration is greater than 4.4 mmol/L (80 mg/dL), percentage of results with deviations from the reference value within $\pm 20\%$);

B = the number of pairs of the deviation of sensor value from primary sensor minus YSI value is within ± 20 mg/dL /total number of pairs) * 100% (when the blood glucose concentration is less than or equal to 4.4 mmol/L (80 mg / dL), percentage of results with deviations from the reference value within ± 1.1 mmol/L (20mg/dL).

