7.8 Numbers of Reading in the Low and High Ranges

Every effort to safely collect data in the low and high range via the hyperglycemic and hypoglycemic challenge will be made.

The number and percentage of YSI values collected when Sensor readings displayed 'Low' (less than 40 mg/dL) and 'High' (greater than 400 mg/dL) will be provided.

This part of indicators will be summarized by descriptive statistics. The analysis method will be referred to section 7.2.

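### Does the primary agreement rate lose certain misses because the plan gives no rule for Low and High sensor readings?

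*SAP*

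**What the plan says.** - **Primary rate (SAP 5.2).** Agreement is a count, "the number of pairs of the deviation of sensor value from primary sensor minus YSI value is within" a limit, divided by the total number of pairs. The limit is ±20% when the reference is above 80 mg/dL and ±20 mg/dL at or below it.
- **Test (Protocol 14.9; SAP 7.6).** A one-sample t test on subject-level rates. The study passes if the 97.5% lower confidence limit exceeds 60%.
- **Pairing (SAP 6.6.2; same text in Protocol 14.8.2).** Each reference value is matched to the closest sensor value less than 5 minutes away. A separate sentence says "Most of descriptive analyses will include all YSI values", subject to a sensor condition of at least 40 *or* at most 400 mg/dL. Readings outside that range are noted as "displayed to users as Low or High without numerical numbers".
- **Missing data (SAP 6.5).** "No imputations will be done for missing data".
- **Data source.** The endpoints "will be based on retrospective data collected from primary sensor" (SAP 6.6.1). Protocol 7.2.4 says the CareLink iPro software will "merge sensor and BG meter data to produce glucose sensor values".
- **Exclusions (Protocol 14.9).** The item "Justification for Exclusion of Particular Information from the testing of the Hypothesis" is answered as not applicable.
- **Reporting (SAP 7.8).** The report will give "The number and percentage of YSI values collected when Sensor readings displayed 'Low' (less than 40 mg/dL) and 'High' (greater than 400 mg/dL").

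**The concern.** The primary rate needs a number from the sensor, and the plan says that a Low or High reading shows none. With no imputation allowed, a programmer might treat such a reading as forming no pair and leave it out. The device's own output would then decide whether a miss counts in the endpoint that decides success. Some of these misses are certain: a sensor reading Low while YSI is 100 mg/dL fails the 20/20% rule whatever the hidden number is.

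The plan also expects low and high glucose. SAP 7.8 refers to hypoglycaemic and hyperglycaemic challenges and schedules a Low/High count, but it does not say how those readings are scored. Two programmers could therefore build different primary datasets, and a choice made after the data were seen could affect the pass/fail result.

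**Working it through.** **1. The plan's own figure.** Inputs from SAP 6.2: null mean 0.60, expected mean 0.72, SD 0.32, one-sided 0.025, power 80%. With t quantiles on n − 1 degrees of freedom, n = 0.32² × (2.0025 + 0.848)² / 0.12² = 57.8, so 58, as stated. Noncentral-t power at 58 is 0.802. The standard error is 0.32/√58 = 0.0420, so the smallest observed mean that passes is 0.60 + 2.0025 × 0.0420 = 68.4%.

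**2. Which saturated pairs are certain misses.** From the limits in SAP 5.2:
- Low (<40): for YSI 60 to 80, agreement needs a sensor value of at least YSI − 20, hence at least 40. For YSI above 80 it needs at least 0.8 × YSI, hence above 64. Low is a certain miss when YSI ≥ 60.
- High (>400): agreement needs a sensor value of at most 1.2 × YSI. High is a certain miss when YSI ≤ 400/1.2 = 333 mg/dL.
- Low with YSI below 60, or High with YSI above 333, may agree or not. At YSI 45, for example, any sensor value from 25 to 39 agrees.

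**3. Effect if such pairs were dropped.** Let f be the share of pairs dropped and a the share of those that would have agreed. With a true all-pairs rate of 0.60, the analysed rate is (0.60 − f × a)/(1 − f). The documents give neither f nor a, so both are assumed. The formula carries over to the subject-level test if f and a are the same in every subject, and the SD is held at 0.32. The chance of passing (nominal 2.5%) is then:

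| a | f = 0.5% | f = 1% | f = 2% | f = 5% |
|---|---|---|---|---|
| 0 (all certain misses) | 2.9% | 3.5% | 4.7% | 11.1% |
| 0.3 | 2.7% | 2.9% | 3.5% | 5.6% |
| 0.6 | 2.5% | 2.5% | 2.5% | 2.5% |
| 0.8 | 2.4% | 2.2% | 2.0% | 1.4% |

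For a = 0 the analysed rates are 0.603, 0.606, 0.612 and 0.632. Dropping favours the device only when fewer than 60% of the dropped pairs would have agreed.

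**4. Effect of the strictest alternative.** Suppose every saturated pair were scored as a miss and 0.72 is a rate among numeric pairs only. The mean becomes 0.72 × (1 − f) = 0.716, 0.713, 0.706 and 0.684 for the same four shares. Power falls from 0.80 to 0.78, 0.75, 0.70 and 0.50.

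**5. Does the text drop these pairs?**
- The pairing sentence sets a time window and no sensor range.
- The range condition is confined to most descriptive analyses. Because it is joined by *or*, every number satisfies it, so read literally it excludes nothing.
- Where a range limit is wanted it is stated outright: the same section restricts the Clarke grid to YSI values of 40 to 400 mg/dL.
- Where data are to leave the primary endpoint, the SAP says so: section 6.6.4 names primary endpoints when it removes sensor data beyond 144 hours.
- Protocol 14.9 lists no exclusions from the test.
- The no-imputation rule concerns missing data. A Low or High reading was observed; only its exact size is hidden.
- The remark on Low and High describes what users see. The analysis uses values produced by software after download, and no passage says whether that export stops at 40 and 400.

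**The case for a change.** The best case for a change is that the plan has one pass/fail endpoint and no scoring rule for a reading type that it expects. The answer in Protocol 14.9 is not a complete guide, because SAP 6.6.3 and 6.6.4 do remove data, and it gives no score for a reading without a number. SAP 6.6.4 names the primary endpoint, whereas the range sentence in 6.6.2 does not, so a reader is left unsure. SAP 7.8 again speaks of readings displayed as Low or High, so the export may hold no number. If such readings form no pair, a subject with nothing else would leave the efficacy population. If the other subjects average 72%, one such subject at 0% among 58 would put the true mean at 0.72 × 57/58 = 70.8%, and two would put it at 69.5%. A rule written in advance would be cheap.

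Of this, the silence of the text stands, and so does the arithmetic. That the pairs would be dropped remains an inference from a display note and a missing-data rule, against several passages that point to keeping them. The larger figures also need shares for which the documents give no support: 11.1% requires one pair in twenty to be a certain miss.

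**Conclusion.** The gap is one of detail. Following the plan as written is not shown to give a wrong primary result, and its natural reading keeps the pairs. An analyst has an obvious course: use the exported number where there is one; otherwise keep the pair, count it as non-agreement where the 20/20% rule makes that certain (Low with YSI ≥ 60, High with YSI ≤ 333 mg/dL), and show the remaining pairs under both bounds. The counts in SAP 7.8 let a reader see how many YSI values are affected.

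Making all non-agreement the primary rule for the indeterminate pairs would be a debatable trade. It penalises readings that may be right and, on the assumptions in step 4, costs up to 30 points of power (0.80 to 0.50 at 5%). The *or* in the range condition and the not-applicable entry in Protocol 14.9 are clerical slips.

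Size and direction are unknown. The figures rest on assumed saturated shares, equal in every subject, and an SD fixed at 0.32. If these readings cluster in a few poor sensors, both the mean and the SD would shift differently. If the 60% threshold was meant for numeric pairs only, dropping the others inflates nothing. The silence would matter if the export held no numbers outside 40 to 400 and such readings were common; the documents show neither.
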